### 11.4.3 Secondary Analyses

The socio-demographic and clinical characteristics of the participants will be described using standard descriptive statistics (frequencies, medians and interquartile ranges, or means and standard deviation). Other comparative analyses at the 9-months and 2-years endpoints will be performed using chi-square test (or Fisher's test when appropriate) for categorical variables, and paired t-test or Wilcoxon signed-rank test for continuous variables, depending on the distribution of the variable. Time-to-event outcomes will be assessed using Cox proportional hazards with adjustment for baseline risk factors. Factorial analysis will enable to measure the effect on all outcomes of the intervention made to the first and the second dose of MMR, separately or in combination.

The infection outcomes of the 2-year endpoint will be analysed in two stages:

1) first we will examine the infection count distributions in the 4 experimental conditions: standard schedule (Group C.C.), early first dose (Group M.C.), separated 2nd dose (Group C.M.), both intervention (Group M.M.). We will check if the effects of one intervention appear similar across strata of the other intervention. This will be done to identify strong qualitative interactions (e.g., absence of effect in one stratum versus presence in the other), and to guide the regression models.

2) then we will use negative binomial regression models, starting with a model that includes an interaction term:

$\log(\text{infections}) = b_0 + b_1 \cdot \text{early} + b_2 \cdot \text{separate} + b_3 \cdot \text{early} \cdot \text{separate}$  where "early" and "separate" designate the 2 components of the intervention, both coded as 0 or 1. We will consider the coefficient  $b_3$  to decide on further analysis. If  $b_3$  is of small magnitude (in clinical and scientific terms) we will conclude to the absence of a statistical interaction (on a multiplicative risk scale), and we will drop the interaction term from further analysis. If  $b_3$  is of substantial size, further analysis will proceed as though the trial was a 4-arm trial, with 3 interventions (Group M.C, Group C.M. and Group M.M.) compared to the standard schedule arm (Group C.C.). The assessment of  $b_3$  will be based primarily on scientific and clinical relevance, not on statistical significance.

Model in absence of interaction:

$\log(\text{infections}) = b_0 + b_1 \cdot \text{early} + b_2 \cdot \text{separate} (+ \text{any other adjustment variables})$

The interpretation of the coefficients is

$b_0$ : log of number of infection events under standard schedule (Group C.C.)

$b_1$ : log of relative risk of infection under early first dose, averaged over strata of separate 2nd dose

$b_2$ : log of relative risk of infection under separate 2nd dose, averaged over strata of early first dose

Model if a substantial interaction is detected:

$\log(\text{infections}) = b_0' + b_1' \cdot \text{early} + b_2' \cdot \text{separate} + b_3' \cdot \text{combined} (+ \text{any other adjustment variables})$

The variable "combined" will be set to 1 in the combined intervention arm, and 0 in the other arms

The interpretation of the coefficients will be

$b_0'$ : log of number of infection events under standard schedule (Group C.C.)

$b_1'$ : log of relative risk of infection under early first dose (Group M.C.), versus standard

$b_2'$ : log of relative risk of infection under separate 2nd dose (Group C.M.), versus standard

$b_3'$ : log of relative risk of infection with both components (Group M.M.), versus standard

The other adjustment variables will be defined before closure of the trial, and specified in the statistical analysis plan. They will be variables associated with the risk of infection, such as immune status, having siblings, exposure to day care, etc.

Note on power in presence of interaction:

The power and sample size calculations assumed the absence of an interaction, so that all participants would be used for the estimation of each intervention effect. If an interaction is present

and the second model is used, the effective sample size available for the evaluation of each of the 3 interventions will be halved. This will cause a loss of precision and of power. The confidence intervals for each intervention effect will be widened by a factor 1.4 (square root of 2). We believe that even in such a situation the trial would produce useful knowledge; even if the results were non-significant (statistically) for one intervention or the other, they would facilitate the planning of further trials, and would be available for meta-analysis.

Subgroup analysis are planned (by sex, risk factor, underlying maternal immunity, etc.) and will be detailed in the statistical analysis plan. The null hypothesis is that there is no difference between subgroups, whereas the alternate hypothesis is that the intervention is more beneficial in certain subgroups.

The analyses will be done in collaboration with the Clinical Research Center at Geneva University Hospitals, once all participants have attended the 24 months visit.

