
Statistical Considerations:
	
The full details of the analysis will be provided in the statistical analysis plan, which will be finalised prior to database lock.
 
The primary outcome (number of respiratory infections between 6 and 9 months of age) will be compared between the two groups of 1st MMR timing (Group M.C. and M.M. vs. Group C.M. and C.C.) using negative binomial regressions, adjusted for sex (male/female), day-care attendance (yes/no), presence of comorbidities (yes/no), older siblings (yes/no), and will be presented as adjusted incidence rate ratios (aIRRs) with 95% confidence intervals.
 
Other comparative analyses at the 9-months and 2-years endpoints will be done using chi-square test (or Fisher's test when appropriate) for categorical variables, and paired t-test or Wilcoxon signed-rank test for continuous variables, depending on the distribution of the variable. Time-to-event outcomes will be assessed using Cox proportional hazards with adjustment for baseline risk factors.
 
For the 2-years endpoints, factorial analysis will enable to measure the effect on all outcomes of the intervention made to the first and the second dose of MMR, separately or in combination.
 
Regression will be used to identify independent factors associated with each of the outcomes. All significant predictors (<math>p < 0.20</math>) will be then included in a stepwise backward multivariate analysis.
 
Trauma and accident outcomes will also be compared between the two groups and will act as control events, as MMR is not believed to change their risk of occurrence.
 
Subgroup analysis are planned (by sex, risk factor, underlying maternal immunity, etc.).
 
The analyses will be done in collaboration with the Clinical Research Center at Geneva University Hospitals.

GCP Statement:
	
This study will be conducted in compliance with the protocol, the current version of the Declaration of Helsinki, ICH-GCP, as well as all national legal and regulatory requirements.

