### 6.2 Methods of minimising bias

#### 6.2.1 Randomisation

Consent to blood tests at 6, 9 and 24 months of age will be sought, and will determine whether a child participates in Part 1 only, or both Part 1 and Part 2. Participant will be randomly allocated at inclusion to four equal groups, using a web-based randomisation procedure, stratified by consent to blood tests (yes/no), in randomly permuted blocks of variable length (4 or 8), enabling to prevent predictability of intervention assignments. The randomisation lists will be generated prior to the initiation of the study by someone not involved in the study analysis and will be integrated into REDCap.

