#### 7.1.2 Exclusion criteria

The presence of any one of the following [exclusion](#) criteria will lead to exclusion of the participant:

- 1) Contra-indications to MMR, including
  - a) immunosuppression (i.e. proven, suspected, or planned)
  - b) allergy to a component of the vaccine
  - c) receipt of a live-attenuated vaccine in the four weeks prior to inclusion
- 2) Vaccine refusal
- 3) Indication for an early MMR vaccination, including
  - a) Measles outbreak
  - b) Planned immunosuppression (indication to an accelerated schedule to be completed before starting an immunosuppressive treatment)
  - c) Travel to a region with a high risk of measles outbreak
- 4) Indication for vaccination with MMR-varicella (MMRV) instead of MMR, including
  - a) severe eczema
  - b) parental will
- 5) Parental inability to follow the procedures of the study, e.g. due to language problems, psychological disorders, known/suspected non-compliance, substance abuse, etc.
- 6) Plan to move out of the country or have prolonged absence during the trial
- 7) Other sibling included in the trial
  - a) In the case of multiple pregnancy, only one child can be randomised.
- 8) Any temporary contra-indication to MMR, including child being sick (active significant illness)
  - a) Inclusion can be delayed a few days until the illness resolves

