### 11.2 Determination of Sample Size

The sample size calculation for the clinical outcome (500 participants) is based on the primary outcome of respiratory infections. Based on the data from a previous trial, we expect a rate of respiratory infection of 0.29 episodes per month (SD 0.32) between 6 and 9 months of age in the control groups (Group C.M. or C.C.). By randomising 500 participants, we will have an 80% power to detect a minimum of 30% reduction in this incidence with a 2-sided p-value of 0.05, assuming at least 85% completion rate of the 9 months questionnaire. The 500 participants will be randomised into 4 groups of similar size (see Section 6 and table 3 in Section 8.1): for the primary outcome analysis, the 250 children receiving early MMR at 6 months of age (Group M.C. or M.M.) will be compared with the 250 children receiving the regular MMR at 9 months of age (Group C.M. or C.C.).

		Timing of the 2 nd MMR		
		2 nd MMR 1m after the 12y DPT-PCV (Modified)	2 nd MMR concomitant to the 12y DPT-PCV (Current)	
Primary outcome comparing the timing of the 1 st MMR	1 st MMR at 6m (Modified)	Group M.M., n=125	Group M.C., n=125	N=250
	1 st MMR at 9m (Current)	Group C.M., n=125	Group C.C., n=125	N=250
		N=250	N=250	

Table 7. Participant allocation in 4 groups; for the primary outcome analysis, the Groups M.C. and M.M. will be compared with the Groups C.M. and C.C. C: current MMR schedule; DTP: diphtheria-tetanus-pertussis vaccine; m: month; M: Modified MMR schedule; PCV: pneumococcal conjugate vaccine.

The sample size calculation for the laboratory outcomes (100 participants) is more conservative as it depends on the success of the blood collection and of the laboratory processing for each of the time points. The use of paired samples (taken from the same infant at different ages) reduces the effect of inter-individual heterogeneity and provides greater statistical power with lower participant numbers.

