Among the 500 participants enrolled, 100 participants consenting to blood collection (Part 2) will be randomised into 4 groups of similar size (table 2 in Section 6.1): for the laboratory outcome analysis, the 50 children receiving early MMR at 6 months of age (Group M.C. or M.M.) will be compared with the 50 children receiving the regular MMR at 9 months of age (Group C.M. or C.C.). Assuming that at least 60% of participants from Part 2 will provide a sufficient blood sample at each time point, which will then be processed without any problem, these 100 participants in total are required for Part 2, to ensure that a minimum of 30 participants per group of 1st MMR timing (30 in Group M.C. or M.M., and 30 in Group C.M. or C.C.) could be included in all analyses.

		Timing of the 2 nd MMR		
		2 nd MMR 1m after the 12y DPT-PCV (Modified)	2 nd MMR concomitant to the 12y DPT-PCV (Current)	
Primary outcome comparing the timing of the 1 st MMR	1 st MMR at 6m (Modified)	Group M.M., n=25	Group M.C., n=25	N=50
	1 st MMR at 9m (Current)	Group C.M., n=25	Group C.C., n=25	N=50
		N=50	N=50	

Table 8. Participant allocation in 4 groups; for the laboratory outcome analysis, the Groups M.C. and M.M. will be compared with the Groups C.M. and C.C. C: current MMR schedule; DTP: diphtheria-tetanus-pertussis vaccine; m: month; M: Modified MMR schedule; PCV: pneumococcal conjugate vaccine.

**Cytokine secretion & ICS studies:** with a minimum of 30 participants per group of 1st MMR timing (30 in Group M.C. or M.M., and 30 in Group C.M. or C.C.) who could be included in all analyses (minimum of 60 in total) we would have >80% power to detect a biologically significant 1.5-fold-change in cytokine responses at the 5% significance level, based on the variance of previous infant cytokine and ICS studies.

**Transcriptomic analysis:** a minimum of 20 participants per group of 1st MMR timing (20 in Group M.C. or M.M., and 20 in Group C.M. or C.C.; 40 participant in total) provides 80% power to detect a 1.25 fold-change in RNA expression counts for RNASeq.

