#### 11.4.1 Datasets to be analysed, analysis populations

The groups will be compared by intention-to-treat analysis. Sensitivity analysis will be done using an as-treated (per-protocol) analysis and will only include participants with available data who received the interventions as planned.

Subgroup analysis are planned (by sex, risk factor, underlying maternal immunity, etc.) and will be detailed in the statistical analysis plan.

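### Only paired tests are named for continuous secondary outcomes, although the randomised groups are independent and no pairs exist across arms

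*Protocol*

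**What the plan says.** Section 11.4.3 of the protocol opens its comparative plan with: "Other comparative analyses at the 9-months and 2-years endpoints will be performed using chi-square test (or Fisher's test when appropriate) for categorical variables", and continues "and paired t-test or Wilcoxon signed-rank test for continuous variables, depending on the distribution of the variable". The Statistical Considerations row of the synopsis repeats the choice: "paired t-test or Wilcoxon signed-rank test for continuous variables, depending on the distribution of the variable". No unpaired test for a continuous variable is named anywhere in the protocol.

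The design is one of independent groups:

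- Section 6.2.1: "Participant will be randomly allocated at inclusion to four equal groups, using a web-based randomisation procedure". The blocks are of length 4 or 8, stratified only by consent to blood tests, with no matching.
- Section 7.1.2 excludes a child with a sibling in the trial and adds: "In the case of multiple pregnancy, only one child can be randomised".
- Section 11.4.1: "The groups will be compared by intention-to-treat analysis".

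The only pairing described is in section 11.2, for the Part 2 blood samples: "The use of paired samples (taken from the same infant at different ages) reduces the effect of inter-individual heterogeneity". Even there, the laboratory comparison is between groups: "the 50 children receiving early MMR at 6 months of age (Group M.C. or M.M.) will be compared with the 50 children" in the other first-dose arm.

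**The concern.** A paired t-test or signed-rank test needs a defined partner for each observation, and across these arms there is none. In the synopsis the sentence follows directly on the primary comparison between the two first-dose groups, and the word other carries that comparison forward. The categorical tests in the same sentence are for independent groups; a sentence about within-child change would need a paired categorical test such as McNemar's. The natural reading is therefore a between-group comparison with the wrong family of tests.

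An analyst following the text has two options. One is to pair unrelated children by their order in the file, which makes the p-value depend on a sort and leaves children out when the arms differ in size. The other is to pair each child with itself at an earlier age, which answers a question about maturation. At stake is the interpretation of continuous secondary outcomes that have no other written model, most clearly at 9 months.

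**Working it through.** **1. The protocol's own sizing treats the arms as independent.** Inputs from section 11.2: control rate 0.29 episodes per month, SD 0.32, 30% reduction (difference 0.3 × 0.29 = 0.087), 80% power, two-sided 0.05, 85% completion. The independent two-sample formula gives

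n per arm = 2 × (1.960 + 0.842)² × 0.32² / 0.087² = 212.4, so 213.

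Allowing for loss: 213 / 0.85 = 250.6, so 251 per arm and 502 in total, against 500 stated. The planned size is reproduced without any pairing.

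**2. Pairing across arms: what changes and what does not.** The mean of the n cross-arm differences equals the difference in arm means, whatever the pairing. Only the standard error moves, through the sample correlation r that the row order happens to create. With equal SDs,

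paired t = two-sample t / √(1 − r), where r has mean 0 and SD about 1/√(n − 1).

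The two data sets below are illustrative: standardised normal values, with differences chosen to put the two-sample p just under 0.05. The differences are assumptions, not figures from the protocol.

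- 30 v 30 (the minimum analysable Part 2 size), difference 0.55 SD: two-sample t = 0.55 × √(30/2) = 2.13, p = 0.037. The SD of r is 1/√29 = 0.186, so 95% of pairings give r within ±0.364. Paired t then runs from 2.13/√1.364 = 1.82 (p = 0.078) to 2.13/√0.636 = 2.67 (p = 0.012).
- 212 v 212 (85% of 250), difference 0.20 SD: two-sample t = 0.20 × √(212/2) = 2.06, p = 0.040. The SD of r is 1/√211 = 0.069, so r lies within ±0.135. Paired t runs from 2.06/√1.135 = 1.93 (p = 0.055) to 2.06/√0.865 = 2.21 (p = 0.028).

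Re-pairing each data set at random 2000 times agrees:

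| Size | Test | Full range of p | Central 95% of p | Share below 0.05 |
|---|---|---|---|---|
| 30 v 30 | paired t | 0.002 to 0.100 | 0.013 to 0.078 | 68% |
| 30 v 30 | signed-rank | 0.0006 to 0.237 | 0.011 to 0.119 | 49% |
| 212 v 212 | paired t | 0.021 to 0.063 | 0.028 to 0.054 | 90% |
| 212 v 212 | signed-rank | 0.006 to 0.176 | 0.015 to 0.095 | 67% |

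The unpaired tests give one answer each: t 0.037 and rank-sum 0.044 at 30 v 30; t 0.040 and rank-sum 0.039 at 212 v 212.

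**3. Average behaviour of the paired t-test across arms.** In 20,000 simulated trials of 212 per arm (negative binomial counts over three months with dispersion 0.068, which matches the planning SD), rejection with no effect was 4.8% for both the paired and the two-sample t-test. With means of 0.87 v 0.65, power was 71.4% for both. The tests disagreed at 0.05 in 0.5% of null trials and in 1.8% under that effect. A separate run gave 4.6% v 4.7%, and 70.7% for both.

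**4. Unequal arms.** With, for example, 215 and 209 completers the paired test cannot be computed unless 215 − 209 = 6 children are left out.

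**5. Pairing within child.** Assume no vaccine effect, 30 infants per arm, a maturation shift of 0.5 SD in both arms and a within-child correlation of 0.5. The SD of the change is √(2 − 2 × 0.5) = 1, so the expected paired t is about 0.5 × √30 = 2.74. In simulation the within-arm paired test was significant in 76% of trials, and the between-arm two-sample test in 4.8%.

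**The case against.** The best defence has four parts.

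First, the protocol does plan within-child comparisons. Serial samples are taken at 6, 9 and 24 months, and AIM8 in section 9.2.2 asks for both a comparison with pre-vaccination values and one between groups. Paired tests are correct for the former, and section 9.2 says the control group serves to separate age effects from vaccine effects. This stands, but the sentence is not limited to that use and nothing is named for the between-group half.

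Second, the sentence is not the only route to the randomised contrast. Section 11.4.3 also promises factorial analysis of all outcomes, and the outcome sections promise factorial and multivariate analyses of clinical and laboratory outcomes. Time-to-event outcomes go to Cox models and 2-year infection counts to negative binomial regression. A reader might infer that every continuous secondary outcome is left with an invalid test; the documents do not support that. The synopsis, however, ties the factorial analysis to the 2-year endpoints, and the only model written out is for infection counts, so the gap at 9 months remains.

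Third, a reader might infer that a cross-arm paired p-value does not test the randomised comparison, or that error rates are inflated. Steps 2 and 3 of the working show otherwise for the t-test: it targets the same difference in means, with essentially the same average type I error and power. The charge of answering a different question holds only for within-child pairing.

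Fourth, section 11.4 calls itself brief and defers detail to a later analysis plan. But this is a method stated in two places, not one left open, and an analysis plan that named unpaired tests would have to depart from the protocol.

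**Conclusion.** Wrong as written, and it should be fixed; it does not threaten the trial's main result. The primary outcome, the 2-year infection counts and the Cox outcomes are unaffected. The exposed results are continuous secondary outcomes without another written model, such as days free of event and SCORAD or POEM at 9 months.

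The harm is of three kinds: p-values that depend on row order, children left out when arms are unequal, or a test of ageing in place of a test of schedule. The first matters only near the threshold and more in small groups: at 30 v 30 the central 95% of paired-t p-values ran from 0.013 to 0.078 for one data set, against 0.028 to 0.054 at 212 v 212. These ranges rest on data sets deliberately placed near p = 0.05, so they show what can happen and not how often. The step 3 simulation uses the primary outcome's planning values, which this sentence does not govern, and a 25% reduction (0.65/0.87 = 0.75) in place of the planned 30%. The 76% in step 5 depends on the assumed maturation shift and correlation.

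The wording may be a slip for unpaired and rank-sum, but the documents do not say so.

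**What to change.** Amend section 11.4.3 and the synopsis together:

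- For between-group comparisons of continuous outcomes, use a two-sample t-test or Wilcoxon rank-sum test, or linear regression on randomised arm adjusted for the pre-randomisation value where one was measured (SCORAD at Visit 1, baseline blood in Part 2).
- At 2 years, include both factorial terms (early first dose, separate second dose).
- Summarise per-event measures such as episode duration per child, or use a method that allows for repeated events in the same child. A plain two-sample test on events would ignore that clustering.
- Keep the paired t-test and signed-rank test only for within-child change, as in the Part 2 serial samples.

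The cost is a short wording change in two places. Sample size, randomisation, visits and data collection stay as they are.

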### 6.4 Risk mitigation of the trial design

**Variability in infectious risk:** Individual risk of infection depends on host (predisposition) and environmental (exposure) factors. Randomisation should ensure that risk factors are equally distributed between the two groups. The risk of those factors influencing the outcomes is also addressed by adjusting the analyses by the presence of comorbidities (host predisposition), siblings and day-care attendance (environmental exposure).

**Recruitment:** Recruitment will be through a network of private paediatricians highly motivated in contributing to clinical research. Pamphlets will be distributed in maternity services and paediatricians' offices; infants will be recruited during the first few months of age and parents will have opportunity to ask questions before the randomisation visit at 6 months of age. With over 5000 live births per year in Geneva, a minimum acceptance rate of 5% for Part 1 (questionnaires only) and of 1% for blood testing will enable recruitment to be completed in 18 months.

**Study burden / acceptance of the study:** The online questionnaire is being designed in partnership with parents in order to make it as user-friendly as possible. It will be completed every 2 weeks by participants' parents on a smartphone, computer or tablet following a participant-specific link sent by text or email, and will take less than 10 minutes to complete. The questionnaire includes many fields per participant but, thanks to branching algorithms, only items relevant to each participant will be displayed (based on the answers to previous questions). This design reduces redundancy and reduces the risk of missing or duplicate data.

**Accuracy of parent-reported data:** The questionnaire uses pre-filled fields, drop-down menus, and other measures to reduce the time taken for completion, and to increase the accuracy of the data. The data will be reviewed with the treating paediatrician, and the parents during the clinic visit, to retrieve any missing information. The child's medical records will also be checked. Clinical assessment will take place during the study visit to confirm some of the outcomes (e.g. presence of eczema using validated scores).

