### 9.2 Assessments of outcomes

#### Clinical outcomes

##### Source of information:

- 1) Online parent questionnaires sent every two weeks for the first 3 months, then monthly.
- 2) Contact with the treating paediatrician at 9 and 24 months for completion of any missing illness data.
- 3) Access to medical records.

The data collected (Table 4) will enable the extraction of the following measurement for each participant for both infectious and allergic episodes: number of episodes between 6 months and 2 years of life, interval between inclusion and first episode, characteristics of each episode (e.g. diagnosis, duration) and treatment (e.g. type, route, duration), complications, hospitalisation (e.g. reason, length of stay, outcomes), number of days free of episode. Episodes of trauma/accidents will be used as control events.

Data collected at inclusion, confirmed with treating paediatrician and hospital records
Demographics: parental age, education, ethnicity, country of birth; household composition, age of siblings; location of home (countryside, urban); socioeconomic group; date of birth*.
Potential confounding and or mediating factors pre-randomisation: maternal pregnancy factors (mode of delivery, infection, antibiotics, probiotics, smoking, supplements, vaccines), infant factors (sex, gestational age, season of birth, sepsis, antibiotics, probiotics, alimentation, supplements and medications); family history of allergic disease (eczema, hay fever, asthma, food and non-food allergies); household smoking; pet exposure.
Data collected with online questionnaires, confirmed with treating paediatrician and hospital records
Infection outcome data: episodes of: upper/lower respiratory tract infection (including croup, pharyngitis, otitis media, bronchiolitis, bronchitis, pneumonia), cold sores/mouth ulcers, gastroenteritis, urinary tract infection, bone-joint infection, other infection.  For all infections: diagnosis, pathogen(s), site of infection, date, symptoms, duration, severity, outcome, health care use, hospital admission (more than 1 day), treatment.
Trauma/accident data (used as control events): medically attended accidents, burns or trauma.  For all occurrences: date, severity, health care use, hospital admission (more than 1 day).

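### One joint two-year model for both MMR doses leaves infections before the second-dose arms diverge to dilute the second-dose effect, or to distort the first-dose effect if used as a covariate

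*Protocol*

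**What the plan says.** Section 11.4.3 sets out the two-year infection analysis: "then we will use negative binomial regression models, starting with a model that includes an interaction term". The terms are *early*, *separate* and their product. If the product term is judged small it is dropped, and b2 is then the "log of relative risk of infection under separate 2 nd dose, averaged over strata of early first dose". If it is judged substantial, a four-arm version with coefficients b1', b2' and b3' is fitted. Further adjustment variables, described as predictors of infection risk such as siblings and day care, are left to the SAP.

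The outcome is called only the 2-year endpoint. AIM3 (Section 4.3) places the second-dose question at 13 to 24 months. Sections 5.2 and 9.2.2 define the infection outcomes for AIM1 and AIM3 together over 6 to 24 months.

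All four groups are randomised at 6 months (Section 7.3). In Table 3 the two second-dose schedules do not differ before the 11-12 month visit. Infections are recorded throughout: "Online parent questionnaires sent every two weeks for the first 3 months, then monthly" (Section 9.2). Section 6.4 notes that "Individual risk of infection depends on host (predisposition) and environmental (exposure) factors".

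**The concern.** For the second-dose factor, a child's infections from 6 to about 11 months precede any difference in schedule. They carry no information on the effect, but they do carry information on how infection-prone the child is. For the first-dose factor the same infections come after randomisation and are what the early dose is meant to reduce.

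A single equation cannot treat them properly for both factors. Inside the outcome, they pull b2 towards no effect. Outside the outcome and unused, the information is lost. Used as a covariate, they help b2 but condition b1 on a consequence of the first dose. Choosing covariates in the SAP does not resolve this, because a covariate added to the printed equation enters for both coefficients.

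The stake is Stage B. The clinical sample size in Section 11.2 rests only on the 6-9 month primary outcome, so the second-dose comparison has no power calculation of its own.

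**Working it through.** **Inputs from Section 11.2.**
- Rate and SD: "we expect a rate of respiratory infection of 0.29 episodes per month (SD 0.32) between 6 and 9 months of age".
- Total and power: "By randomising 500 participants, we will have an 80% power".
- Target effect and level: a 30% lower rate, two-sided 0.05.
- Completion: 85% at 9 months.
- Allocation: "The 500 participants will be randomised into 4 groups of similar size", hence 250 against 250 for each factor.

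**1. The plan's own figure.** The difference is 0.30 × 0.29 = 0.087. Per arm, n = 2 × (1.96 + 0.842)² × 0.32² / 0.087² = 213, or 426 in total. Dividing by 0.85 gives 502, which agrees with 500. With 212.5 per arm, power is 80.0%. The sample size reproduces.

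**2. Between-child variation implied by the SD.** Reading 0.32 as the SD of each child's three-month average rate, the three-month count has mean 0.87 and SD 0.96. The negative binomial dispersion is k = (0.9216 − 0.87) / 0.87² = 0.068.

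**Assumptions for the rest.** The rate is 0.29 per month at all ages, with constant frailty. There are 212.5 children per level at 24 months (the protocol gives no completion figure beyond 9 months). The second-dose rate ratio is 0.80 from 13 months and 1 before. The early dose acts at 6-9 months only, with rate ratio 0.70.

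**3. Dilution.** Of 18 months of follow-up, 7 precede 13 months. The apparent rate ratio on a 6-24 month count is (7 + 11 × 0.80) / 18 = 0.88. A true 0.70 would show as (7 + 11 × 0.70) / 18 = 0.82.

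**4. Power for b2.** The variance of the log rate ratio is [(1/m₀ + k) + (1/m₁ + k)] / 212.5, where m₀ and m₁ are the mean counts in the two arms.
- 13-24 months, k = 0.068: m₀ = 3.19, m₁ = 2.55, SE 0.063, z = 0.223/0.063 = 3.55, power 94%.
- 6-24 months, k = 0.068: m₀ = 5.22, m₁ = 4.58, SE 0.051, z = 0.130/0.051 = 2.57, power about 73%.
- Simulation at k = 0.068: 75% against 94%, with other runs at 70% and 74% for the 6-24 month count.
- Simulation at k = 0.5: 34% against 67%, with other runs at 37% and 38% against 70%.

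**5. Gain from the pre-dose count as a covariate.** With 5 months before (mean 1.45) and 11 after (mean 3.19), the squared correlation ρ² of the two counts is the largest share of variance that can be removed.

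| k | ρ² | simulated variance reduction |
|---|---|---|
| 0.068 (protocol SD) | 0.016 | about 1% |
| 0.25 (assumed) | 0.12 | about 10% |
| 0.5 (assumed) | 0.26 | about 23% |
| 1 (assumed) | 0.45 | about 41% |

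Other runs, with different coding of the covariate and handling of the dispersion, gave 0-1%, 7-11%, 21-23% and 28-45%. At k = 0.068, power for a rate ratio of 0.80 stays at 94%.

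**6. Distortion of b1.** With the outcome counted from 13 months and a true b1 of 0, adding the pre-dose count moved b1 to about +0.02, +0.05, +0.07 and +0.10 on the log scale at k = 0.068, 0.25, 0.5 and 1 (up to +0.11 across runs). A null first dose would read as a rate ratio of 1.02 to 1.12. b2 stayed unbiased.

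**The case against.** The strongest reply is that covariates are deferred to the SAP, the list is open, and AIM5 already names previous infections as a factor to study. Nothing excludes the prior count. If the outcome starts at 13 months, the count may enter and b2 is valid, provided b1 is not read from that fit. This stands, and it limits the point: the joint equation fails only when both coefficients are read from it. Reading b2 alone from such a fit amounts to the separate model proposed here, which the protocol does not state.

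It can also be said that 6-24 months is simply the span covering AIM1 and AIM3 together. That is a fair reading, but Section 11.4.3 does not say which window serves which coefficient.

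A reader might infer that the prior count would sharply improve precision. The documents do not support that. On the protocol's SD the gain is about 1%, and siblings and day care would absorb part of any larger gain. The SD does concern respiratory infections at 6-9 months only, so variation for other infections or ages is unknown.

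A reader might also infer that all 500 children supply the count at no cost. They do not: 15% non-completion is allowed by 9 months, and Section 14.1 permits follow-up to stop after that visit.

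Finally, the trial is open-label and parents receive the vaccination plan at 6 months (Section 9.3.2), so pre-dose reporting could in principle be coloured by knowledge of the second-dose arm. That caveat stands. Comparing pre-dose counts between the second-dose arms would show any such difference.

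**Conclusion.** The point holds as a worthwhile improvement to a secondary analysis. It does not touch the primary analysis, and it does not show that b2 would be invalid: a 6-24 month count is still a randomised comparison, but of a diluted effect.

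The main loss comes from the window. At the protocol's own SD, power for b2 is about 75% instead of 94% if infections from 6 months are counted, and the apparent rate ratio is 0.88 instead of 0.80. The covariate is a minor addition at that SD and becomes material only at assumed k of about 0.25 or more.

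These sizes rest on an assumed rate ratio of 0.80, a constant rate and frailty, and 85% completion carried to 24 months. The structural conclusion, that one equation cannot serve both coefficients once the pre-dose count is used, does not depend on them.

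**What to change.** Reconcile the windows in Section 4.3 (AIM3) and Sections 5.2 and 9.2.2, and state in Section 11.4.3 which window serves which coefficient. Then specify two models.

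- **Second dose.** The outcome is infections from a common age after the second-dose arms diverge (13 months per AIM3), with an offset for follow-up time. The terms are *separate*, *early*, the baseline covariates, and log(6-11 month count + 1) with the months observed. Report only b2 and, if fitted, the *early*-by-*separate* product term.
- **First dose.** Report b1 from a model without the pre-dose count. Do the same for the four-arm contrasts b1' and b3', since both contain the first-dose effect.

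The cost is protocol and SAP wording, one extra model, a rule for children with incomplete pre-dose follow-up, and the slight inconvenience that b1 and b2 come from different fits. No new data are needed.
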